### **I. Abstract - Summary of the study background, aims, and design.**

Central themes in person-centered care are dignity/respect/choice for the care recipient.

This SBIR Phase 1 clinical study is a minimal risk study that focuses on how the new technology, DevaWorld (DW), can support and amplify these principles, while assisting care staff.

DevaWorld is an interactive assistive technology developed with user-centered design principles, mirroring fifteen evidence-based non-pharmacological interventions for people living with Alzheimer's disease and its related dementias (AD/ADRD). Built with a game engine and deployed on a tablet device, DevaWorld is a purpose-built virtual world depicting activities of daily living (ADLs). It contains interactive engagement stimuli, including customized digital artifacts that hold meaning to the person.

During a DevaWorld session (DWS), both the care-partner and care-receiver (dyad) are active participants. Preliminary evidence shows that DWS sessions support the psychosocial wellbeing of people living with dementia (PLWD). Informally collected data lead us to the current study, in which we measure the impact of DevaWorld ADLs on actual ADLs. We hypothesize that undertaking ADL-related virtual activities will support completions of actual ADLs, thereby increasing effectiveness and improving care outcomes.

The aims of this mixed-method, single-arm study are to (1) demonstrate the feasibility (tolerability and acceptability) of DevaWorld within daily routines, and (2) evaluate the effectiveness of DevaWorld sessions in preparing PLWD for specified ADLs. Endpoints are: evidence of the dyads' acceptance of DevaWorld, a reduction in ADL-related care challenges compared to baseline, and overall durations of time spent on the ADLs compared to baseline.

## **II. Background and Significance**

*The current environment that is the basis for the proposed research, including a presentation of the problem, a critical evaluation of current knowledge and a description of how this proposal will enhance this knowledge.*

The significance of improving ADL capacity has a cascading effect across the entire dementia care ecosystem. Research correlates the inability to accomplish ADL with lower quality of life (1, 2) and increased health care costs (3). ADL dependency requires more resources, and the risk of increased morbidity and mortality is higher than those who are ADL-independent (4) (5) Dependency can be the direct result of insufficient capacity to provide adequate daily assistance to care-recipients, accounting for 49% of the total direct costs associated with Alzheimer's disease and related dementias (AD/ADRD) (6). Care staff are curtailed by time pressures and inadequate training, which diminish PWLD's autonomy and dignity leading to lower self-esteem and reduced value in others' eyes (7–9). Inadequate attention to personhood can evoke confusion, fearfulness, disorientation, aggression and apathy in the person impacted by dementia (10, 11), adding to care staff stress and job dissatisfaction (12). Staff departures and costly turnovers often follow, further eroding the care services sector (13). Scales & Lepore (2020) compute that from 2018 to 2028, the workforce is expected to add 1.3 million jobs, and an additional 6.9 million jobs will become vacant as existing workers leave the field or exit the labor force. These figures indicate the pressing need to reduce staff stressors to forestall what they describe as "an escalating national crisis of unmet need for long-term services and supports" (p.2). Combined, these factors contribute to the \$305 billion currently paid by Medicare for dementia care (14). However, this figure does not fully scope the magnitude of the socioeconomic burden of AD/ADRD, which AARP surmises will be unsustainable as the AD/ADRD population grows (15).

By deploying our novel site of virtual environments, DevaWorld, which contains ADL-related engagement stimuli, this proposal will advance understanding of how technology-based interventions can mitigate negative responses to ADLs for increased satisfaction within the dyad, greater effectiveness and better care outcomes. This evidence will be used to support DevaWorld's value within the long-term care services sector and advance our case as an FDA-credentialed digital therapeutic.

## **III. Study Aims**

*The purpose of the study, including identification of specific primary objectives/hypotheses.*

The purpose of the study is to show evidence of DevaWorld's value in long-term care settings. Our primary objective is to show that DevaWorld's virtual ADLs support real-world ADLs resulting in more manageable, more effective ADL completions. We hypothesize that a DWS reduces behavioral responses and care partner stress to achieve this outcome.

The aims are to:

- (1) demonstrate feasibility (tolerability and acceptability) of DWS within the dyad
- (2) evaluate the effectiveness of DevaWorld sessions for preparing PLWD for specified ADLs

#### **IV. Administrative Organization**

Mentia DTx, Inc. is the grantee. It is the entity responsible for the research and development of DevaWorld. Mentia DTx provides project management and data management services. The PI, [name] PhD, is a Mentia DTx employee.

The participating study sites with IRB approval will be

- (1) assisted livingcommunity for older adults, 90% of whom experience cognitive decline.
- (2) assisted living memory care community or similar.

#### **V. Study Design**

##### *a. Experimental design of the study*

This mixed-methods single-arm eight-week feasibility study (Phase I) monitors approximately forty residents and their usual care staff across two residential care communities. We will use both quantitative and qualitative methods will be used to produce data sets for analyses.

##### *b. Study population general description*

The study population is long-term care residents aged 65 years and older, with moderate to moderate to severe dementia, according to the Global Deterioration Scale for Assessment of Primary Degenerative Dementia (GDS) (Reisberg, 16).

##### *c. Sample size determination and power analyses*

We target a 95% confidence level for our study. For a confidence interval of 15%, the sample size is 32. A 15% confidence level is sufficient for a feasibility study.

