##### *d. Study outcomes/endpoints*

The study outcome will be a body of evidence that supports our hypothesis: that interactions with ADL content inside the graphical interactive virtual world, DevaWorld, supports completions of actual ADLs.

DevaWorld's feasibility (Aim 1)

Successful primary outcomes are >55% DWS-participation rate and a statistically significant difference between assessments of DWS-participation and non-participation, indicating tolerability and acceptability of routine DWS.

DevaWorld as an assistive tool for preparing and completing ADLs. (Aim2)

Successful secondary outcomes are:

- a reduction in ADL-related care challenges compared to baseline
- reduced time spent on ADLs compared to baseline
- a reduction in negative response behaviors associated with the ADL
- greater interest in the ADL
- a positive shift in care staff attitudes

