## VI. Study Procedures

### a. Subject Selection Procedures

#### i. Sampling plan including Inclusion/Exclusion criteria

We will use convenience and purposive sampling (22) to recruit residents from our testsites in the United States.

We determine our sample size to be 40 in anticipation of 20% dropout rates, which concurs with similar studies. We estimate that a sample size of 32 would allow us to determine the tolerability, acceptability, and feasibility of DW sessions based on similar pilot studies conducted for technological interventions in Alzheimer's disease (18).

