- Following baseline and prior to the intervention phase, participating staff will take part in group training, with extra support as needed.
- During the intervention phase, a period of six weeks, the same dyads (or as close to same as is practical) will be assigned a schedule incorporating DWS followed by the same ADL routine as baseline.
- Each resident-participant will have two DWS per week. Staff-participants will spread this load across their shifts, averaging eight DWS sessions per 5-day week. We anticipate that session durations will average five minutes with variability according to resident-participants' individual interest levels on a given day. Staff schedule during study:

Mon 1h 10m	Tue 55m	Wed 1h 10m	Thu 55m	Fri 1h 10m
Res A DWS	Res A Mouth Care	Res A DWS	Res A Mouth Care	Res A Mouth Care
	Res B Mouth Care		Res B DWS	Res B Mouth Care
Res A Mouth Care	Res C DWS	Res A Mouth Care		Res C DWS
Res B DWS		Res B Mouth Care	Res B Mouth Care	
Res C Mouth Care	Res C Mouth Care	Res C Mouth Care	Res C Mouth Care	
Res B Mouth Care	Res D Mouth Care	Res D DWS	Res D Mouth Care	Res D DWS
Res C Mouth Care				
Res D Mouth Care		Res D Mouth Care		Res D Mouth Care
Reporting				

- Procedure for running a DWS

- **Initiating a session:**

Prior to the ADL, the dyad will sit in a quiet nook or the resident's bedroom with appropriate lighting. The care staff will ask the resident if they are comfortable (e.g. need a drink, need to go to the toilet, is comfortably dressed, has glasses and hearing aids in place).

To initiate the session, the care staff will open DevaWorld on the tablet device and invite resident to join.

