## IX. Analysis Plan

*Describe statistical analysis methods as appropriate. For example, will intention-to-treat methodology be used in the analysis? Will there be any sample stratification?*

- Thematic and sentiment analysis of tablet-recorded spoken and visual exchanges during DWS and post-session comments
- Statistical and text analyses of questionnaire responses
  - Statistical Analysis Plan
    - Assessment inventories with scores on the inventory's scale
    - Measuring mean value and standard deviation for the group
    - Complete a superiority statistical test
    - P-values calculated by t-test, 1 sided

HIPAA-compliant data capture software; eg REDCap, will be used to create the database and analyses. <https://www.project-redcap.org/>

Data will be reported graphically or with summary measure (e.g., means and standard errors or median and 95% confidence intervals), and subjected to statistical analysis when appropriate. Completion rates and grades scores will be presented as proportions and percentages.

ADCS-ADL scores will be compared from end of baseline to biweekly scores to the end of intervention and may be analyzed using a paired Student's t-test or the Wilcoxon signed-rank test if the data are not normally distributed.

Completion rates will be the percentage of all dyads who complete the entire eight weeks of study. The ratio of positively graded scores per dyad will be calculated to obtain the level of satisfaction of dyads and indicate the acceptability of DWS.

Aim 1: Successful primary outcomes are >55% completion rate and a statistically significant difference between assessments of completers and non-completers, indicating tolerability and acceptability of routine DWS.

Aim 2: The secondary outcome is to determine the feasibility of DevaWorld as an assistive tool for preparing and completing ADLs. Improved dyad outcomes are less time to complete ADLs, a reduction in negative response behaviors associated with the ADL, greater interest in the ADL, Care staff indicates tasks are easier than before.

Outcomes measures for baseline and intervention will be the same. As the score sheets cover a broader range of ADLs than those depicted in DW, overall and individual ADL scores will be analyzed and subjected to statistical tests. Our null hypothesis will be no statistical differences between ADL scores during the intervention and baseline phases

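### The sample size of 32 is tied to 95% confidence and a 15% interval with no expected proportion; near the 55% pass mark 32 gives about ±17 points, and the rate condition carries no confidence limit

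*Combined protocol and SAP*

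**What the plan says.** Section V.c targets 95% confidence and continues: "For a confidence interval of 15%, the sample size is 32". It then adds: "A 15% confidence level is sufficient for a feasibility study". It gives no expected proportion, formula or endpoint, and does not say whether 15% is a half-width or a full width.

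The sampling plan (VI.a.i) inflates 32 for attrition: "We determine our sample size to be 40 in anticipation of 20% dropout rates". It also supports 32 by precedent, as enough to judge "feasibility of DW sessions based on similar pilot studies conducted for technological interventions", without a precision figure.

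Aim 1 success is stated twice. V.d: "Successful primary outcomes are >55% DWS-participation rate and a statistically significant difference between assessments of DWS-participation and non-participation". The Analysis Plan (IX): "Successful primary outcomes are >55% completion rate and a statistically significant difference between assessments of completers and non-completers". For the second rate, IX fixes the denominator: "Completion rates will be the percentage of all dyads who complete the entire eight weeks of study". IX plans to show completion as proportions and percentages. It mentions 95% intervals only as one example of general summary reporting, attached to medians.

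**The concern.** Precision is the only quantitative basis given for the sample size. For a single proportion, the number needed depends on the expected rate, and V.c does not state one. The rate that matters most for the decision is 55%, close to the worst case for precision, so ±15 points has to be checked there.

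The rate condition in V.d and IX is judged on the observed percentage alone. The other Aim 1 condition is a significance test between groups of participants; it puts no limit on the rate. A reader could therefore take a pass as evidence that the true rate exceeds 55% when the data do not show that, with no planned interval to warn them.

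**Working it through.** **Inputs.** Confidence 95%, read as two-sided (z = 1.96); d = 0.15, read as a half-width; n = 32 (all V.c). Dropout 20% and 40 enrolled (VI.a.i). Threshold above 55% (V.d, IX). Denominator for completion: all dyads, about 40 (IX). The expected proportion p is not given and has to be varied.

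**Step 1. Can 32 be reproduced?** Use n = z²p(1−p)/d².

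- p = 0.50: 1.96² × 0.25 / 0.0225 = 42.7, so 43.
- p = 0.55: 1.96² × 0.2475 / 0.0225 = 42.3, so 43.
- p = 0.75: 1.96² × 0.1875 / 0.0225 = 32.01.
- p = 0.80: 1.96² × 0.16 / 0.0225 = 27.3, so 28.

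Other readings:

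- One-sided 95% at p = 0.50: 1.645² × 0.25 / 0.0225 = 30.06, so 31.
- Finite population of 125 at p = 0.50: 42.68 / (1 + 41.68/125) = 32.0.
- 15% as a full width (d = 0.075, p = 0.50): 170.7, so 171.

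So 32 follows from p near 0.75 or a population of about 125, and a one-sided bound comes close. None of these is stated. The attrition step does reproduce: 32 / 0.80 = 40.

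**Step 2. Precision actually delivered.** Two-sided 95% half-width, 1.96 × √(p(1−p)/n), in percentage points:

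| True rate | n = 32 | n = 40 |
|---|---|---|
| 50% | 17.3 | 15.5 |
| 55% | 17.2 | 15.4 |
| 75% | 15.0 | 13.4 |
| 80% | 13.9 | 12.4 |

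**Step 3. What the rate condition lets through.** With 40 dyads, 22/40 is exactly 55% and fails, so the smallest passing result is 23/40. Exact (Clopper–Pearson) two-sided 95% intervals:

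- 23/40 (57.5%): 41% to 73%
- 28/40 (70.0%): 53% to 83%
- 29/40 (72.5%): 56% to 85%

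Results from 23 to 28 therefore pass with 55% inside the interval. With independent dyads, P(X ≥ 23) is 21% at a true rate of 50% and 44% at 55%. These are upper bounds on the chance of Aim 1 success, because the second condition must also be met.

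**Step 4. Shared staff (assumption, not in the documents).** VI.c.ii has each staff member "averaging eight DWS sessions per 5-day week", with two sessions per resident, so about 8 / 2 = 4 residents each. If residents of the same staff member are correlated, the design effect is 1 + 3 × ICC. At n = 40 and 55%, the half-width is 15.4 × √(1 + 3 × ICC): about 16.5 points at ICC 0.05, 17.6 at 0.10 and 19.5 at 0.20.

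**The case against.** The strongest reply is that no arithmetic error has been shown. A rate of 75% gives 32. So does a modest finite population, which is plausible with only two communities. The planned 20% dropout implies about 80% completion, where 32 gives ±13.9, better than claimed; at that rate 40 independent dyads would meet the rate condition more than 99.9% of the time. Completion is counted over all dyads, so 40 is the relevant number, and ±15.4 at 55% is close to 15. Judging a feasibility mark on the observed rate is a legitimate design choice, and the 15% confidence level is plainly a slip of wording.

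Much of this stands. It cannot be said that 32 is wrong, only that it rests on something unwritten. The shortfall at n = 40 is under half a point by the formula in step 2; the ±17 belongs to the 32 that V.c itself pairs with 15%. But 80% retention does not explain 32 either, since it gives 28, and VI.a.i uses the dropout to go from 32 to 40, not to derive 32. The reply also leaves the rate condition untouched. A point-estimate pass mark is acceptable, but the plan does not commit to showing the uncertainty beside it.

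**Conclusion.** The concern holds and should be fixed. The stated precision cannot be reproduced from the plan. At 50 to 55% it is about ±17 points for the 32 named in V.c and about ±15.5 for all 40; it is met at rates of about 75% and above. The label in V.c conflicts with the 95% level given just before it. The rate condition can be met by any of 23 to 28 of 40 without showing that the rate exceeds 55%.

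These figures assume two-sided 95% intervals, a half-width reading of 15%, and independent dyads counted once each. V.d names participation and IX names completion; the figures for 40 apply to completion. V.d defines no denominator for participation, so its precision cannot be fixed from the plan. The correlation range in step 4 is illustrative and the conclusion does not depend on it.

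**What to change.** In V.c, replace the sizing sentence with:

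> With 32 residents the two-sided 95% confidence interval has a half-width of about 17 percentage points, and with all 40 enrolled about 15.5, at a rate of 50 to 55% (about 14 and 12 at 80%).

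In the sentence after it, call the 15% a margin of error and make it agree with these figures.

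In IX, add:

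> The exact 95% confidence interval for the completion rate over all enrolled dyads will be reported beside the 55% threshold. A result whose interval includes 55% will be described as not having shown that the rate exceeds 55%.

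Put the same interval beside the participation rate in V.d, once its denominator is defined. If participation is counted per session, use a resident-level or cluster-robust interval.

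The cost is a few sentences and one reported interval per rate. No residents are added, and the pass mark and sample size stay. The stated precision looks less favourable near the threshold, and a result of 23 to 28 of 40 carries a caveat.

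A stricter rule is open to the sponsor but is not needed for this fix: require the one-sided 95% lower limit to exceed 55%, which means 28/40 (lower limit 56.0%). With independent residents it would pass 3.9% of the time at a true 55%, and 58%, 82% and 96% of the time at 70%, 75% and 80%. If it were adopted, the caveat should use the same one-sided limit, because 28/40 passes one-sided but not two-sided.

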##### *d. Study outcomes/endpoints*

The study outcome will be a body of evidence that supports our hypothesis: that interactions with ADL content inside the graphical interactive virtual world, DevaWorld, supports completions of actual ADLs.

DevaWorld's feasibility (Aim 1)

Successful primary outcomes are >55% DWS-participation rate and a statistically significant difference between assessments of DWS-participation and non-participation, indicating tolerability and acceptability of routine DWS.

DevaWorld as an assistive tool for preparing and completing ADLs. (Aim2)

Successful secondary outcomes are:

- a reduction in ADL-related care challenges compared to baseline
- reduced time spent on ADLs compared to baseline
- a reduction in negative response behaviors associated with the ADL
- greater interest in the ADL
- a positive shift in care staff attitudes

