**Consent/No consent:**

As the app opens, the care staff will obtain verbal consent (resident uses affirming, positive words or sounds) or non-verbal consent (resident smiles/nods/leans toward the tablet/touches care staff in a positive way/agrees to touch the screen either independently with care staff's support).

If no consent, the caregiver will reapproach in 3-5 minutes, again check if the

person is comfortable, and make any adjustments to improve comfort. Care staff will seek consent again. If consent is not given a second time, the DWS will be dropped and the usual ADL routine will begin.

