**Ongoing Participation or Refusal:**

Staff will record the resident's attitude to the DWS in their daily report. The research team will review these reports daily.

Refusal may be communicated verbally (using negative or anxious words or sounds) or non-verbally (shrugging, shaking head, pushing the tablet away, refusing to put hand to the tablet, not permitting the care staff to hold their hand to support screen tapping, turning their body away, looking away from the app, passive disinterest

If a resident-participant decides that they no longer want to be involved in the study, not just the DWS session for the day, they will be offered DWS sessions daily. After 7 consecutive days of refusals, they will be withdrawn from the study.

(Guidance on the Process Consent method is covered during training and is described below.)

- Plan for 5 mins per session
- Upon consent, care staff initiates the DWS and guides the resident to the part of DevaWorld where the interactive ADL will be explored
- Following the resident's lead in pace and interest, the dyad focuses on helping the DevaWorld characters (male or female) to manage self-care activities in DevaWorld's bathroom and getting him/her ready for bed.
- The session will end when the resident seems ready
- Upon completion of a session, the care staff assists the resident, if needed, to select an emoticon on the end screen before ending the DWS.
- After completing the DWS, the care staff will initiate the planned ADL task, and observe their resident's interactions, cooperation, mood and any behavioral responses.
- Process Consent (21). This method is used during DevaWorld sessions.
  - Staff participant checks consent prior, during and after DW session.  
If Subject indicates their withdrawal of consent, Staff stops and lets the resident withdraw before or during the activity
  - If the resident no longer wants, or is no longer able, to be involved.  
The staff observes residents wishes (verbally or non-verbally) to guide the next steps. Staff then informs the researcher.
  - Depending on the situation, it may or may not be appropriate to ask the resident again later if they would like the opportunity to get involved., The caregiver will reapproach in 3-5 minutes, again check if the person is comfortable, and make any adjustments to improve comfort. Care staff will seek consent again. If consent is not given a second time, the DWS will be dropped and the usual ADL routine will begin.
- Assessments, tools  

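### Sections V.d and IX give different primary success criteria for Aim 1 (session participation versus eight-week completion), and the participation rate is never defined

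*Combined protocol and SAP*

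**What the plan says.** Two current sections each set the Aim 1 success criterion.

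- Section V.d (Study outcomes/endpoints): "Successful primary outcomes are >55% DWS-participation rate and a statistically significant difference between assessments of DWS-participation and non-participation". The plan nowhere says what counts as participation, or whether the unit is a session, a resident or a dyad.
- Section IX (Analysis Plan): "Successful primary outcomes are >55% completion rate and a statistically significant difference between assessments of completers and non-completers". The rate is defined there: "Completion rates will be the percentage of all dyads who complete the entire eight weeks of study".

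Both sentences close by saying that the result indicates tolerability and acceptability of routine DevaWorld sessions (DWS). Section IX also plans a per-dyad share of favourable grades as a sign of acceptability.

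The procedures in section VI.c.ii bear on how the two rates relate:

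- There are two baseline weeks without DWS, then six intervention weeks with two DWS per resident per week.
- On a refused session: "If consent is not given a second time, the DWS will be dropped and the usual ADL routine will begin". Nothing there calls this withdrawal.
- On withdrawal: "After 7 consecutive days of refusals, they will be withdrawn from the study". This rule is written for residents who wish to leave the study altogether, as distinct from skipping a day's session.
- The staff partner in a dyad may change where keeping the same one is not practicable.

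Section VI.a.i sets enrolment at 40, allowing for 20% dropout.

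**The concern.** Both halves of the criterion differ. The rate in V.d concerns taking part in sessions, while the rate in IX is retention over eight weeks, two of which contain no sessions. The comparison in V.d could be made within residents, by session or by day. The comparison in IX is between dyads. Neither criterion sentence names the assessment to be compared or its unit.

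This is the rule by which the trial declares its primary outcome met. With two versions in force and one of them undefined, the verdict may depend on which section is followed, and nothing in the plan prevents that choice being made after the data are seen.

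**Working it through.** **The plan's own figures.** Enrolment reproduces: 32 / (1 − 0.20) = 40. The 55% threshold is not derived anywhere, so there is nothing to reproduce for it.

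**Inputs from the documents.** 40 residents and 20% dropout (VI.a.i); 2 DWS per week for 6 weeks (VI.c.ii); threshold above 55% (V.d and IX).

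**Assumptions.** Participation is read as sessions held divided by sessions scheduled. All 40 residents enter the intervention phase. Session uptake is illustrative, because the plan gives no expected uptake.

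1. Scheduled sessions: 2 × 6 = 12 per resident; 12 × 40 = 480 in all.
2. Counts needed to pass:
   - Completion: 22/40 is exactly 55%, so at least 23/40.
   - Participation: 0.55 × 480 = 264, so at least 265/480.
3. Illustration at the planned dropout (32 complete, 8 leave), with 6 sessions per completer and 2 per dropout:
   - Completion: 32/40 = 80%, pass.
   - Participation: (32 × 6 + 8 × 2)/480 = 208/480 = 43.3%, fail.
   - If V.d instead counts residents with at least one session, the same data give 40/40 = 100%, pass. The undefined unit therefore matters within V.d alone.
4. Range of uptake at 32 completers. With x sessions per dropout, completers must average more than (264 − 8x)/32 sessions for participation to exceed 55%:
   - x = 0: 8.25 of 12
   - x = 2: 7.75 of 12
   - x = 6: 6.75 of 12

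   Below these averages the two rates disagree; above them both pass.
5. The reverse conflict needs dropout well above plan. With 20 of 40 completing at 11 sessions each and 20 leaving after 6 each, completion is 50% (fail) and participation is (220 + 120)/480 = 340/480 = 70.8% (pass).
6. Chance that the IX rate threshold is met, with X the number of completing dyads, binomial with n = 40 and independent dyads, P(X ≥ 23):
   - 20% dropout: 0.9997
   - 30% dropout: 0.968
   - 40% dropout: 0.689

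**The case against.** The strongest reply is that this is one criterion in loose wording. The two sentences share their opening, their threshold, their two-part structure and their closing phrase, and IX supplies a definition that V.d lacks. On that reading no conflicting verdict follows, and the defect is mismatched wording with a missing definition. The reading is plausible, but no passage states it, and the refusal and withdrawal procedures treat declining a session and leaving the study as different events. Even if it is right, the two sections still have to be aligned.

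The objection does rule out three stronger readings that a reader might infer:

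- *That the plan's own assumptions predict opposite verdicts.* Only the 80% retention is planned. The uptake of 6 and 2 sessions is assumed, and the conflict arises only under a session-level reading.
- *That the primary outcome is almost certain to be met under IX.* The figure of 0.9997 concerns the rate alone, at 20% dropout and with independent dyads. IX also requires a significant difference, and the probability falls as dropout rises.
- *That IX judges acceptability by retention alone.* It also calculates the per-dyad share of favourable grades, and VI.c.ii describes an end-of-shift questionnaire on tolerance and acceptance. The criterion sentences do not name either one as the assessment compared, but both are in the plan.

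**Conclusion.** Wrong as written: an internal inconsistency in the primary success criterion. V.d and IX state different rates and different comparisons for Aim 1, nothing in the plan equates or ranks them, and the V.d rate is undefined. The documents do not show which section should prevail.

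The inconsistency rests on the text alone. Its possible size rests on the session-level reading and assumed uptake: at the planned dropout, 80% completion can stand beside 43% participation. At that same dropout the IX rate threshold is close to a foregone conclusion, so by itself it hardly tests whether residents accept the sessions.

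**What to change.** Before data are analysed, state one Aim 1 criterion in identical words in V.d and IX, with its numerator, denominator, unit and analysis set. Report the other rate descriptively.

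If a session-level rate is chosen:

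- divide by all scheduled sessions and keep dropouts in the denominator;
- say how residents lost during baseline are counted, since the IX rate covers all eight weeks;
- count separately sessions refused at the start, sessions stopped by refusal once under way, and sessions carried through. VI.c.ii recognises refusal during a session, so counting every session begun would include those abandoned at once.

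In either case, name one assessment and its unit for the comparison, in both sections. The per-dyad share of favourable grades (IX) and the tolerance and acceptance questionnaire (VI.c.ii) are candidates already in the plan. State also whether a change of staff partner counts as dyad non-completion.

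The cost is wording in two sections and a few fields in a report that already exists: "Staff will record the resident's attitude to the DWS in their daily report". The staff report is the natural source for the consent outcome, because consent is sought while the app is opening ("As the app opens, the care staff will obtain verbal consent") and the listed app data include no consent outcome. The other cost is that the reported rate may be less favourable than retention.
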